## 5.7 Duration of Follow Up

Subjects will be contacted by phone once between 30 and 45 days after termination of study treatment or until death, whichever occurs first. Patients removed from study for adverse event(s) will be followed until resolution or stabilization of the adverse event.

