### 1.2. Secondary Objectives

A. All cohorts: Calculate the incidence of reported CTCAE v 4.03 adverse events and abnormal laboratory test results

B. All cohorts: Estimate the overall response rate (ORR) per RECIST version 1.1, time to tumor progression (TTP), PFS at 8 weeks and 16 weeks, overall survival (OS), disease-specific survival (DSS)

C. Cohorts A and B, after crossover: Assess PFS, RR, TTP, OS, and DSS following administration of regorafenib in the open label portion of the study.

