## **4. REGISTRATION PROCEDURES**

### **4.1 General Guidelines**

Subjects enrolling on this clinical trial must meet all inclusion and exclusion criteria. Exceptions will not be granted.

Data will be entered via a web portal into a SARC study specific database. While all study evaluations must be performed by the Investigator as described in Section 9, Study Evaluations and Study Calendar, only data related to the primary and secondary endpoints, as well as safety data, will be captured in the eCRFs.

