## 5.6 Duration of Therapy

Treatment may continue until one of the following criteria applies:

- Disease progression as defined by RECIST 1.1
- Greater than 28 days have elapsed since the last dose of study drug
- Patient decides to withdraw from the study during the treatment phase of the study
- Patient decides to withdraw from the study during the follow up phase after completion of treatment on the study
- General or specific changes in the patient's condition render the patient unacceptable for further treatment in the judgment of the investigator.

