**Follow up phone call 30-45 days after off study visit date**

- Interval history
- Concurrent medications.

NOTE: Patients removed from study for adverse event(s) will be followed until resolution or stabilization of the adverse event.

To reiterate: Visits may occur  $\pm 2$  days of the scheduled date,  $\pm 3$  days for weeks of bank holidays. Tumor measurements and reimaging may be done  $\pm 7$  days of the anticipated date.

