## **11.5 Premature termination of study**

This study may be closed prematurely for any of the following reasons:

- If risk-benefit ratio becomes unacceptable owing to, for example:
  - Safety findings from this study (e.g. SAEs)
  - Results of any interim analysis
  - Results of parallel clinical studies
  - Results of parallel animal studies  
(on e.g. toxicity, teratogenicity, carcinogenicity or reproduction toxicity).
- If the study conduct (e.g. recruitment rate; drop-out rate; data quality; protocol compliance) does not suggest a proper completion of the trial within a reasonable time frame.

The investigator has the right to close his/her center at any time.

For any of the above closures, the following applies:

- Closures should occur only after consultation between involved parties.
- All affected institutions (e.g. IEC(s)/IRB(s); competent authority(ies); study center; head of study center) must be informed as applicable according to local law.
- In case of a partial study closure, ongoing subjects, including those in post study follow-up, must be taken care of in an ethical manner.

Details for individual subject's withdrawal can be found in **Section 5.8**.

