## **12. STATISTICAL CONSIDERATIONS**

### **12.1 Efficacy and safety variables**

#### **12.1.1 Efficacy variables**

Efficacy variables to analyze include:

- Progression free survival (PFS, as assessed by RECIST 1.1), defined as time from randomization (or 1st day of treatment, cohort C, D and E) to site determined radiographic tumor progression or death from any cause (whichever occurs first). For patients alive without progression, censoring occurs at the date of last tumor assessment. In PFS analyses, if the exact progression date is unknown, the date of progression is taken to be the date the first time at which progression can be declared
- Proportions of patients who are progression-free (and alive)
- Proportions of patients without progression or death at landmark times (in particular at 8 and 16 weeks)
- Overall survival is defined as the time from randomization (or 1st day of treatment, cohorts C, D and E) until death from any cause. Censoring occurs at the date of last contact.
- Disease-specific survival is defined as the time from randomization (or 1st day of treatment cohorts C, D and E) until death from sarcoma
- Time to progression (as assessed by RECIST 1.1), defined as time from randomization (or 1st day of treatment, cohort C) to centrally-determined radiographic tumor progression, censoring for death without progression. Progression is defined, according to RECIST 1.1, as a 20% increase from nadir and a minimum of 5 mm increase over the lowest sum, the appearance of one or more new target or non-target lesions, or unequivocal progression of existing non-target lesions determined by radiographic assessment. In TTP analyses, the exact progression date is unknown. Date of progression is taken to be the date the first time at which progression can be declared
- Change in target lesion size. Target lesion size will be measured by imaging methods. Tumor size will be measured as a unidimensional tumor measurement per RECIST 1.1.
- Overall response rate (ORR as assessed by RECIST 1.1) defined as the portion of patients evaluable for response who achieved partial response or better and stable disease or better

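### OS and DSS are secondary endpoints in every cohort, but the plan schedules only one general contact after the off-study visit, so Kaplan-Meier OS can be biased by censoring soon after progression

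*Combined protocol and SAP*

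**What the plan says.** Section 1.2 lists "overall survival (OS), disease-specific survival (DSS") as secondary objectives for all cohorts. For cohorts A and B after crossover it adds: "Assess PFS, RR, TTP, OS, and DSS following administration of regorafenib in the open label portion of the study". Section 12.1.1 defines OS as time to death from any cause and states: "Censoring occurs at the date of last contact".

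Under 5.6 and 5.8, progression is one of the events that ends treatment and removes a patient from study. What follows is set out in three places:

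- 5.7: "Subjects will be contacted by phone once between 30 and 45 days after termination of study treatment or until death, whichever occurs first".
- 9.3: "Follow up phone call 30-45 days after off study visit date", with interval history and concurrent medications as its content.
- 9.4: the calendar ends with the same 30-45 day column.

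Contact runs longer only in special cases: adverse events followed to resolution or stabilization (5.7, 7.1.2), related SAEs (7.2.2) and pregnancy (7.2.3, 11.1.4). Section 11.1.5 requires a death to be reported if it falls during the trial or within 30 days of the end-of-treatment visit.

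Other passages touch on follow-up without scheduling it. Section 4.2 tells sites to review the follow-up requirements. Section 5.6 lists "Patient decides to withdraw from the study during the follow up phase after completion of treatment on the study". Section 11.5 says that "ongoing subjects, including those in post study follow-up, must be taken care of in an ethical manner". Section 12.3 gives a 6-month minimum follow-up for cohorts A and B.

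**The concern.** An OS estimate needs deaths to be found whenever they occur. Here the last scheduled contact is set by the end of treatment, and the usual end of treatment is progression. Patients therefore tend to leave the risk set just as their prognosis worsens. Kaplan-Meier assumes that those who leave have the same later risk as those who stay, and this rule can break that assumption.

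Sarcoma deaths after the call, which are what DSS counts, have no collection rule. In cohorts A and B a placebo patient who crosses over stays under observation through a second treatment period, while a regorafenib patient does not. The two arms can therefore be censored at different points in the disease course, and an OS comparison could partly reflect the contact rule.

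**Working it through.** **The plan's own figures.** The documents give no OS or DSS event target or power. The only formal event target is 42 PFS events per randomized cohort. By Schoenfeld's formula, 4(1.645 + 1.282)² / (ln 0.4)² = 40.8, that is 41, close to 42. PFS is censored at the last tumour assessment, so the OS contact rule does not enter this target.

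**Inputs for the illustration.** The median time to progression is 2 months, the control figure in 12.2, so λ = ln 2/2 = 0.3466 per month. Median survival after progression is 7 months (assumed), so h = ln 2/7 = 0.0990. The death hazard before progression is r·h, with r varied. Contact ends g = 1.25 months after progression, about the middle of 30-45 days. There is no crossover. Median OS is then 10.2 months at r = 0 and 8.4 at r = 0.5. That is near the 8-12 months in 2.1, which is only a loose anchor because it runs from diagnosis.

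**Formulas.** Let a = λ + r·h and k = a − h.

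- True OS: S(t) = e^(−at) + (λ/k)(e^(−ht) − e^(−at)).
- Nobody is censored before month g, so the estimate equals S(g) there. Afterwards the risk set holds unprogressed patients and those who progressed within the last g months. The ratio of the second group to the first is q = (λ/k)(e^(kg) − 1), and the progressed share is f = q/(1 + q).
- The hazard that Kaplan-Meier sees is h* = h[r + (1 − r)f]. Estimated OS at 12 months is S(g)·e^(−h*(12 − g)).
- Share of deaths seen: r·h/a + (λ/a)(1 − e^(−hg)).

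**Results at 12 months.**

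| r | f | h* | S(1.25) | Estimated OS | True OS | Deaths seen |
|---|---|---|---|---|---|---|
| 0 | 0.337 | 0.0333 | 0.978 | 0.978 × e^(−0.358) = 0.683 | 0.420 | 12% |
| 0.5 | 0.344 | 0.0665 | 0.929 | 0.929 × e^(−0.715) = 0.454 | 0.354 | 23% |
| 1 | 0.352 | 0.0990 | 0.884 | 0.305 | 0.305 | 31% |

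At r = 0, ending contact at 30 or 45 days instead gives an estimate of 73% or 65%.

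**Falling hazard.** In a separate simulation, median PFS was 2 months, 15% of PFS events were deaths, and median survival after progression was 15 months. The hazard is 0.15 × 0.3466 = 0.052 before progression and ln 2/15 = 0.046 after it, so it falls. Median OS was 14.6 months true and 13.7 estimated.

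**Between arms in A and B (simulation).** Median time to progression was 5 months on regorafenib and 2 on placebo. All placebo patients then crossed over, with a further assumed 5 months to second progression. The shift is the estimated minus the true 12-month OS difference (regorafenib minus placebo).

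| Death hazard during crossover treatment | r = 0 | r = 0.25 | r = 0.5 |
|---|---|---|---|
| post-progression hazard h | 23 points | 15 | 8 |
| on-drug hazard r·h | 7 | 5 | 3 |

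The shift is zero at r = 1. In the second row the estimated difference itself does not favour regorafenib (about −4 to −1 points, against −12 to −4 true). At r = 0.25 and 0.5, deaths also count as PFS events, so model median PFS is 1.87 and 4.24 months, and 1.75 and 3.68 months. These are not the 2 and 5 months of 12.2.

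**The case against.** The strongest reply is that OS is censored at last contact of any kind, not at the scheduled call. Sites may keep contacting patients, and operational detail is deferred in part to an Operations Manual that is not among the documents. Section 4.1 adds that "only data related to the primary and secondary endpoints, as well as safety data, will be captured in the eCRFs", and OS and DSS are such endpoints. It stands that practice may be better than the text, and that the figures above describe the text followed literally. But no passage instructs a later survival contact, and nothing says that the manual covers it.

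It also stands that OS and DSS are secondary and unpowered, that arm-level OS in A and B is confounded by crossover anyway, and that accrual to A-C is complete.

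A reader might infer more than the documents support:

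- That OS is certain to be overestimated. The direction depends on how the death hazard changes at progression, which the documents do not give.
- That the contact rule produces a regorafenib OS advantage of a definite size. That size turns on the death hazard assumed before progression and during crossover treatment, and no document figure settles either.
- That 4.1 or 12.3 promises survival follow-up which 5.7 then contradicts. Section 4.1 does not mention follow-up. The 6 months in 12.3 cover A and B only, stand beside accrual for a PFS-driven analysis, and are not called survival follow-up.

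**Conclusion.** The gap is real and should be fixed. OS and DSS are named endpoints in every cohort, and no general contact is scheduled after one call at 30-45 days. Under literal adherence, and without crossover, 12-month OS could read 68% when the truth is 42%, or 45% when it is 35%, with only 12-23% of deaths seen. With a constant hazard there is no bias, only imprecision. These sizes rest on exponential times, 2 months to progression, an assumed 7-month median afterwards, and contact ending 1.25 months after progression.

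In A and B the bias can differ by arm. In the rising-hazard scenarios tried, it moved the OS difference toward regorafenib by about 3 to 23 points, so no single figure should be claimed. The primary PFS comparison is not affected. Confidence is high that the schedule is missing and limited on the size of its effect.

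**What to change.** Amend 5.7, 9.3 and 9.4 to record vital status, date of death and cause of death by phone or chart check at a regular interval, for example about every 3 months, until death or study closure. Apply this prospectively in D and E: at amendment 6, D was open to accrual and E was being opened (2.5). For patients already off study, make a one-time check where consent allows. In the same amendment, reconcile the starting point of the 30-45 day call, which is end of treatment in 5.7 and the off-study visit in 9.3.

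If this is not adopted, report OS and DSS as limited to the contact window and make no between-arm OS claim from them.

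The cost is about four calls or chart checks per surviving patient per year, with data entry at about 18 centres, and possibly IRB review or renewed consent. No new patients are needed. Patients who withdrew consent cannot be recovered, and crossover confounding of OS in A and B remains.

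As a separate matter, 5.8, 9.3, 9.4 and 10.1 should be reconciled on tumour assessment after treatment stops without progression.

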## 5.8 Criteria for Removal from Study

Patients will be removed from study when any of the criteria listed in Section 5.6 applies. The reason for study removal and the date the patient was removed must be documented in the eCRF including death or lost to follow up.

Subjects **must be withdrawn from the trial** (treatment and procedures) for the following reasons:

- Subject withdraws consent from study treatment and study procedures. A subject must be removed from the trial at his/her own request or at the request of his/her legally acceptable representative. At any time during the trial and without giving reasons, a subject may decline to participate further. The subject will not suffer any disadvantage as a result
- Pregnancy. Pregnancy will be reported as an SAE. (Note: subjects who have been withdrawn from treatment with study drug because of pregnancy should not undergo CT scans [with contrast]/MRI or bone scans while pregnant.)
- If, in the investigator's opinion, continuation of the trial would be harmful to the subject's well-being
- Subject is lost to follow-up
- Death.

Subjects **may be** withdrawn from the study for the following reasons:

- The subject is non-compliant with study drug (regorafenib or placebo), trial procedures, or both; including the use of anti-cancer therapy not prescribed by the study protocol
- Severe allergic reaction to regorafenib (such as exfoliative erythroderma or Grade 3 or 4 hypersensitivity reaction)
- Development of a second cancer
- Development of an intercurrent illness or situation which would, in the judgment of the investigator, significantly affect assessments of clinical status and trial endpoints
- Deterioration of WHO performance status to 4
- Use of illicit drugs or other substances that may, in the opinion of the investigator, have a reasonable chance of contributing to toxicity or otherwise skewing trial result.

Any subject removed from the trial will remain under medical supervision until discharge or transfer is medically acceptable. In all cases, the reason for withdrawal must be recorded in the eCRF and in the subject's medical records.

## **6. DOSING DELAYS/DOSE MODIFICATIONS**

### **6.1 Dose Reduction Levels**

**In adults, the starting dose of regorafenib is 160 mg once daily for Cohorts C, D and E. The starting dose for Cohorts A and B is 4 tablets of regorafenib or placebo daily.**

**For pediatric patients (< 18 years of age), the starting dose is 82 mg/m^2 (rounding to nearest 20 mg), with a maximum daily dose capped at 160 mg. Please refer to dosing table in Section 5.2.**

Study medication will be administered on a 3-weeks on, 1-week off schedule (3 weeks out of every 4).

Doses will be delayed or reduced for clinically significant hematologic and non-hematologic toxicities that are related to protocol therapy according to the guidelines shown in the Dose Delays/Dose Modifications table that follows. In general, this will mean clinically meaningful G 3 or worse toxicity, although clinically significant G 2 toxicity may qualify, according to the treating physician. Dose modifications will follow predefined dose levels. Dose adjustments for hematologic toxicity are based on the blood counts obtained in preparation for the day of treatment.

**Table 6.1.1 Dose reduction levels – adult patients**

The modifications of regorafenib or placebo dosing will follow the following predefined dose levels:		
Dose level 0 (standard starting dose)	160 mg oral daily	Four 40 mg tablets of regorafenib or placebo
Dose level -1	120 mg oral daily	Three 40 mg tablets of regorafenib or placebo
Dose level -2	80 mg oral daily	Two 40 mg tablets of regorafenib or placebo

**Table 6.1.2 Dose reduction levels – pediatric patients**

The modifications of regorafenib or placebo dosing will follow the following predefined dose levels:	
Dose level 0 (standard starting dose)	82 mg/m^2 oral daily, rounding to nearest 20 mg
Dose level -1	72 mg/m^2 oral daily, rounding to nearest 20 mg
Dose level -2	60 mg/m^2 oral daily, rounding to nearest 20 mg

If a subject experiences more than 1 toxicity, dose reduction should be according to the toxicity with the highest grade.

In the case of 2 or more toxicities of the same grade, the investigator may dose reduce according to that deemed most causally related to study treatment.

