Fifteen subjects (36.6%) experienced drug-related TEAEs of worst CTCAE severity Grade  $\geq 3$ , with 11 subjects (26.8% of 41) and 4 subjects (9.8%) having drug-related TEAEs of worst Grades 3 and 4, respectively. Drug-related TEAEs of CTCAE Grade 5 did not occur. Common drug-related TEAEs of CTCAE Grade 3 or above (Grades 3/4), occurring in  $\geq 5\%$  of all 41 treated subjects (by MedDRA preferred term) were thrombocytopenia and rash maculo-papular (7.3% each).

Dose-limiting toxicities were thrombocytopenia at 60 mg/m^2, rash maculopapular at 72 mg/m^2, fever at 82 mg/m^2, and hypertension and erythroderma at 93 mg/m^2. An increased incidence of Grades 3/4 hematological events was observed across dose levels; it appeared that subjects with a history of myelosuppressive therapies such as high dose chemotherapy with stem cell rescue or craniospinal irradiation were at a higher risk for such events.

Overall, 27 out of 41 subjects (65.9%) had at least one dose modification, and the majority of dose modifications were due to AEs; 14 dose reductions (34.1%) were reported for the 41 subjects treated. No subject had more than one dose reduction. Three out of 6 subjects (50.0%), 10 out of 14 subjects (71.4%), 7 out of 14 subjects (50.0%), and 6 out of 7 subjects (85.7%) had AEs leading to dose interruptions in Dose Levels 1, 2, 3 and 4, respectively. The most commonly reported TEAEs (any grade) leading to interruption of study drug in at least 5% subjects of any dose level were pyrexia, platelet count decreased, and rash maculo-papular (7.3% of each). The median duration of regorafenib treatment interruptions or delays (excluding the protocol defined 7 days rest period) was 4 days (range: 1-17 days).

Pharmacokinetics: Regorafenib exposure at all dose levels (60, 72, 82 and 93 mg/m^2) was comparable to that observed in adults; including high inter-subject variability. The observed geometric mean exposure for the 82 mg/m^2 dose group of 50.1 and 47.8 (mg\*h/L), based on nominal and actual dosing, is in the same range as that observed (48.4 mg\*h/L) in adults at the dose level of 160 mg q.d.

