## **6.2 Management of toxicity (other than hand-foot skin reaction, hypertension and LFT abnormalities)**

The table below outlines dose adjustments for **most hematologic and non-hematologic toxicities related to regorafenib** except hand-foot skin reaction (HFSR) and hypertension and LFT abnormalities.

In addition to these recommended dose modifications, subjects who develop diarrhea (see

Section 6.6), mucositis, anorexia or other events predisposing to fluid loss or inadequate fluid intake should be carefully monitored and rehydrated as clinically necessary. This is in order to minimize the risk of postural hypotension and renal failure.

**Table 6.2 Recommended dose modification for most toxicities, except hand-foot skin reaction, hypertension and ALT/AST/bilirubin**

NCI-CTCAE v 4.03 a	Dose Interruption	Dose Modification b	Dose for Subsequent Cycles
Grade (G) 0-2	Treat on time	No change	No change
G 3	Delay until $\leq$ G 2 c	Reduce by 1 dose level	If toxicity remains < G2, dose re-escalation can be considered at the discretion of the treating investigator. If dose is re-escalated and toxicity ( $\geq$ G3) recurs, institute permanent dose reduction.
G 4	Delay until $\leq$ G 2 c	At a minimum, reduce by 1 dose level.  Strongly consider permanent discontinuation for G4 events such as: gastrointestinal perforation/fistula, severe or life-threatening hemorrhage, reversible posterior leukoencephalopathy syndrome, or wound dehiscence.	

a. G: Grade; NCI-CTCAE = National Cancer Institute - Common Terminology Criteria for Adverse Events, version 4.03
 
b. Excludes alopecia, non-refractory nausea/vomiting, non-refractory hypersensitivity and nonclinical and asymptomatic laboratory abnormalities.
 
c. If no recovery after a 4 week delay, treatment should be permanently discontinued unless subject is deriving clinical benefit and is discussed with the SARC Medical Officer.
			

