**Table 6.3.2 Recommended dose modification for hand-foot-skin reactiona**

Grade of event (NCI-CTCAE v 4.03)	Occurrence	Suggested Dose Modification
Grade (G) 1	Any	Maintain dose level and immediately institute supportive measures for symptomatic relief
G 2	1 st occurrence	Consider decreasing dose by one dose level and immediately institute supportive measures. If no improvement, interrupt therapy for a minimum of 7 days, until toxicity resolves to G 0-1 b, c
	No improvement within 7 days or 2 nd occurrence	Interrupt therapy until toxicity resolves to G 0-1. c When resuming treatment, decrease dose by one dose level b
	3 rd occurrence	Interrupt therapy until toxicity resolves to G 0-1. c When resuming treatment, decrease dose by one dose level. b, d
	4 th occurrence	Discontinue therapy
G 3	1 st occurrence	Institute supportive measures immediately. Interrupt therapy for a minimum of 7 days until toxicity resolves to G 0-1. c When resuming treatment, decrease dose by one dose level. b, d
	2 nd occurrence	Institute supportive measures immediately. Interrupt therapy for a minimum of 7 days until toxicity resolves to G 0-1. c When resuming treatment, decrease dose by one additional dose level b, d
	3 rd occurrence	Discontinue treatment permanently.

a. More conservative management is allowed if judged medically appropriate by the investigator.
 
b. If toxicity returns to G 0-1 after dose reduction, dose re-escalation is permitted at the discretion of the investigator if subject has completed one cycle at reduced dose without recurrence of event.
 
c. If there is no recovery after a 4 week delay, treatment with regorafenib or placebo will be discontinued permanently.
 
d. Subjects requiring > 2 dose reductions should go off protocol therapy.
 
e. The maximum daily dose is 160 mg
		

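### Rounding in Table 6.1.2 makes the first paediatric dose reduction empty at some body sizes: levels 0 and −1 give the same daily dose

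*Combined protocol and SAP*

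**What the plan says.** Table 6.1.2 gives three levels for patients under 18: 82, 72 and 60 mg/m², each "oral daily, rounding to nearest 20 mg". Section 5.4 repeats the rounding, caps the dose at 160 mg and allows nothing below 20 mg. The minimum BSA for entry is 0.65 m² (Section 3.1.3).

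Section 6.1 ties changes to these levels: "Dose modifications will follow predefined dose levels". Table 6.2 answers Grade 3 toxicity with a hold and then "Reduce by 1 dose level". Table 6.3.2 does the same for hand-foot skin reaction: "When resuming treatment, decrease dose by one dose level".

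No printed table converts the levels to mg by BSA. Section 6.1 tells sites "Please refer to dosing table in Section 5.2", but Section 5.2 has no dosing table, and Table 5.4 gives only the starting level, in mg/m².

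**The concern.** A dose-level reduction is meant to lower the dose after toxicity. Adult levels are a full 40 mg tablet apart (160, 120 and 80 mg), so each adult step is real. Paediatric levels are 10 and 12 mg/m² apart but are rounded to 20 mg, so two adjacent levels can round to the same daily amount. The protocol does not say to round down on a reduction, to skip a tied level, or that the dispensed dose must be lower. A site that follows the text exactly could hold drug for Grade 3 toxicity, record a reduction, and restart the child on the same dose. No printed table would show that this had happened.

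**Working it through.** **Inputs.** Levels of 82, 72 and 60 mg/m² (Table 6.1.2); rounding to 20 mg and a cap of 160 mg (Section 5.4); minimum BSA 0.65 m² (Section 3.1.3). The protocol prints no mg figures by BSA, so there is no stated result to reproduce.

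**Formula.** Daily dose = min(160, level × BSA rounded to the nearest 20 mg). How exact halves are rounded is an assumption and moves only the band edges.

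**Why ties must occur.** Before rounding, the first step is (82 − 72) × BSA = 10 × BSA mg, which is below 20 mg whenever BSA is below 2.0 m².

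**Where they occur.** Level −1 rounds up to D mg from BSA (D − 10)/72. Level 0 stays at D mg until BSA (D + 10)/82. Between those values the two levels coincide. For D = 60: 50/72 = 0.694 to 70/82 = 0.854. For D = 80: 70/72 = 0.972 to 90/82 = 1.098. The full set is:

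| BSA (m²) | Level 0 (mg) | Level −1 (mg) | Level −2 (mg) |
|---|---|---|---|
| 0.694–0.833 | 60 | 60 | 40 |
| 0.833–0.854 | 60 | 60 | 60 |
| 0.972–1.098 | 80 | 80 | 60 |
| 1.250–1.341 | 100 | 100 | 80 |
| 1.528–1.585 | 120 | 120 | 100 |
| 1.806–1.829 | 140 | 140 | 100 |
| from 2.083 (cap) | 160 | 160 | 120, rising with BSA |

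Example at 1.0 m²: 82 → 80 mg, 72 → 80 mg, 60 → 60 mg. At 0.833 m² (50/60) level −2 also rounds up to 60 mg, so up to 0.854 m² two successive reductions change nothing.

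**Share of the BSA range.** The five bands below 2.0 m² have widths 0.1593, 0.1254, 0.0915, 0.0576 and 0.0237, which sum to 0.4575 m².

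- 0.65–2.0 m²: 0.4575/1.35 = 34%
- 0.65–1.0 m²: (0.1593 + 0.0278)/0.35 = 53%
- 1.35–2.0 m²: (0.0576 + 0.0237)/0.65 = 12.5%

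These are shares of a BSA range. They are shares of patients only if BSA is uniform over that range.

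**The case against.** The arithmetic is not in dispute. The case on the other side is that it matters little, and much of that stands.

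- **Other controls remain.** Under Table 6.2 drug is held until toxicity is Grade 2 or less. It is stopped after four weeks without recovery, unless the patient is benefiting and the case is discussed with the SARC Medical Officer. The Grade 4 row sets one level as a minimum. For hand-foot reaction, "More conservative management is allowed if judged medically appropriate by the investigator". Section 5.8 requires withdrawal if the investigator judges continuation harmful. None of these guarantees a lower dose on restart, and the Grade 3 row of Table 6.2 has no note allowing more caution.
- **Harm is not shown.** A reader might infer that affected children would face avoidable toxicity. The documents do not support that. Section 2.4.3 reports exposure at 60, 72, 82 and 93 mg/m² as "comparable to that observed in adults; including high inter-subject variability", so the benefit of moving from 82 to 72 mg/m² is itself uncertain.
- **Not every toxicity rule is affected.** The paediatric hypertension rules (Table 6.4.2) and the ALT/AST rules (Table 6.5.1) do not use these levels. The gap is confined to Table 6.2 toxicities and hand-foot skin reaction.
- **Second reductions may be rare.** In the phase I study, "No subject had more than one dose reduction", so ties between levels −1 and −2 matter less than ties at the first step.
- **A third to a half of reduced children is not established.** A reader might infer that proportion from the smaller-BSA ranges alone. With BSA between 1.35 and 2.0 m² the share is 12.5%.

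**Conclusion.** The point holds as a minor safety correction. Followed exactly, the protocol's first paediatric reduction leaves the daily dose unchanged in six BSA bands, and at 0.833–0.854 m² the second one does too. Assuming uniform BSA, the first step is empty for about 1 to 5 in 10 children who need it, depending on the BSA range.

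The number of children cannot be estimated well. Only Cohorts D and E still enrol, with funding for 24 patients of all ages, and neither the number under 18 nor their BSA is given. It is likely to be small. No endpoint or decision rule is affected, so nothing here bears on the efficacy conclusions.

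**What to change.** Add to Table 6.1.2: *The first dose-level reduction must lower the dispensed daily dose; if level −1 rounds to the same dose as level 0, give 20 mg less than level 0.* Print the BSA-to-mg table, and correct the reference to Section 5.2 in Section 6.1.

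With this sentence, level −1 is 20 mg below level 0 at every BSA: 60 to 40 mg (0.65–0.854 m²), 80 to 60 (0.854–1.098), 100 to 80 (1.098–1.341), 120 to 100 (1.341–1.585), 140 to 120 (1.585–1.829) and 160 to 140 (from 1.829). Level −1 changes only where it ties with level 0 now.

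The clinical team must set level −2 explicitly in the printed table, as a further 20 mg cut or as discontinuation, wherever level −2 as written is not below the new level −1: 0.65–1.098, 1.167–1.341, 1.500–1.585 and from 2.167 m². A blanket 20 mg rule should not be used there. It would give 40 mg at 0.972–1.098 m² (40/1.0976 = 36.4 to 40/0.9722 = 41.1 mg/m²) and 20 mg at 0.65–0.854 m² (about 23–31 mg/m²), well below 60 mg/m², the lowest phase I level.

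**Cost.** One sentence, one table and one cross-reference in an amendment, with no added visits or patients. The drawback is that the new level −1 falls partly below 60 mg/m²: 40 mg is 46.9–57.6 mg/m² at 0.694–0.854 m², and 60 mg is 54.7–61.7 mg/m² at 0.972–1.098 m². For comparison, level −2 as written already goes down to 40/0.8333 = 48.0 mg/m².
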